6.9. Primary inapparent dengue infection

This condition is defined as a documented seroconversion (anti-dengue IgG antibodies) between two sequential sera samples obtained during the scheduled visits without clinical suspicion of dengue (identified during the time period in which seroconversion occurred).

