7. STATISTICAL ANALYSES

Note that data derivation rules are described in Section 11 and will not be repeated below.

Continuous variables will be summarized with number of non-missing observations, mean, standard deviation (SD), median, minimum, maximum, 25th and 75th percentiles. Categorical variables will be summarized with frequency tables; numbers and percentages for each level will be given.

If an elimination code 900 is attributed, then all the analyses planned to be done on the Total cohort will be done on the Total cohort without subjects with code 900, except Template 5 from EPI-DENGUE-006 BOD BR (116606) TFL (Final analysis) (14-JUN-2019) DRAFT.

The final analysis will be performed on the following study sites using data up to the specified study visits and dengue seasons covered up to study termination:

Region/Study sites name	Initial / Expansion / Replacement cohort	Subject numbers	Study visits covered up to study termination	Dengue season covered up to study termination
Rio	Initial	P - PP	Visit 1 to Visit 6	2015, 2016, 2017, 2018
	Replacement*	PP - PP	Visit 1 to Visit 4	2016, 2017, 2018
Manaus	Initial	PPD - PPD	Visit 1 to Visit 6	2015, 2016, 2017, 2018
	Replacement*	PPD - PPD	Visit 1 to Visit 2	2018
Salvador	Initial	PPD - PPD	Visit 1 to Visit 5	2016, 2017, 2018
Natal	Expansion	PPD - PPD	Visit 1 to Visit 3	2017, 2018
Campinas	Expansion	PPD - PPD	Visit 1 to Visit 2	2018

*only 1 replacement cohort

The following results will be available at the scheduled visits for the following tests:

- Dengue IgG ELISA will be available at Visit 1
- For Visit 2 onwards, Dengue IgG ELISA will be available for subjects with IgG negative at the previous visit.

The following results will be available in case of SDC, for the following tests:

Assays	Result type	Early presenters		Late presenters	
		Acute sample (first visit)	Convalescent sample (follow-up visit)	Acute sample (first visit)	Convalescent sample (follow-up visit)
RT-qPCR	Positive, negative or not typeable DENV type Copies/ml Final classification into positive or negative (used for the dengue case classification)	Yes	TNP	TNP	TNP
NS1 ELISA	Reactive or no reactive	Yes	TNP	Yes	TNP
Dengue IgM ELISA	Reactive or no reactive	Yes	Yes	Yes	Yes
Dengue capture IgG ELISA	Reactive or no reactive	TNP	Yes	Yes	Yes
Hematology / Biochemistry	Numerical results	Yes	TNP	Yes	TNP

TNP = test not performed on the sample as per protocol

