7.2. Analysis of primary and secondary endpoints

7.2.1. Analysis as planned per protocol

The following analyses will be performed overall and by DENV type, study site, gender and age-group previous dengue exposure (Yes = DENV IgG antibodies at previous visit and No = no DENV IgG antibodies at previous visit):

- Incidence rate of *laboratory-confirmed symptomatic dengue infection* with 95% CI for each season separately: the numerator will be the number of subjects with lab-confirmed symptomatic dengue infection during the season (between the visits scheduled before and after the season). The denominator will be the total person-years at risk, i.e. from the visit scheduled before the season until the first RT-qPCR confirmed symptomatic dengue infection during the season, the next scheduled visit or the subject's withdrawal, whichever comes first.

- Incidence rate of *laboratory-confirmed symptomatic dengue infection* with 95% CI all seasons combined: the numerator will be the number of subjects with lab-confirmed symptomatic dengue infection during the study period. The denominator will be the total person-years at risk, i.e. from enrolment until the first RT-qPCR confirmed symptomatic dengue infection, the end of the study or the subject's withdrawal, whichever comes first.

The following analyses will be performed by study site, gender and age-group previous dengue exposure (primary or secondary):

- Incidence rate of *laboratory confirmed or probable symptomatic dengue infections* with 95% CI for each season separately and overall. The numerator will be the number of subjects with symptomatic dengue infection (including laboratory-confirmed and probable cases) during the period. The denominator will be the total person-years at risk.
- Incidence rate of *probable symptomatic dengue infection* with 95% CI for each season separately and overall. The numerator will be the number of subjects with probable symptomatic dengue infection. The denominator will be the total person-years at risk.

The following analyses will be performed by study site, gender and age-group:

- The proportion of subjects with *primary inapparent dengue infection* at each subsequent scheduled visit (not at enrolment) with 95% CI will be calculated as the number of dengue IgG positive cases and at the visit divided by the total number of subjects IgG negative at the previous visit.

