- The proportion of subjects with *secondary symptomatic dengue infection (probable or confirmed)* at each subsequent scheduled visit (not at enrolment) with 95% CI will be calculated as the number of subjects with secondary symptomatic infection since the previous visit divided by the total number of IgG positive subjects at the previous visit.
- The (crude) *seroprevalence of dengue infection* will be calculated at enrolment and at each scheduled visit as a proportion (i.e., the number of dengue IgG positive subjects tested positive at this visit or known to be positive from previous visits divided by the total number of subjects for whom dengue IgG serostatus is known).

Endpoint numerators and denominators are described in [Table 1](#) below:

Table 1 Numerators and Denominators within each strata (DENV type, study site, gender and age-group and previous dengue exposure (primary or secondary))

Analysis	Numerator	Denominator
Incidence rate of laboratory confirmed symptomatic infection by year	All confirmed acute cases during the season (between the visits scheduled before and after the season)	Total person-years at risk, i.e. from the visit scheduled before the season until the first RT-qPCR confirmed symptomatic dengue infection during the season, the next scheduled visit or withdrawal, whichever comes first.
Incidence rate of laboratory-confirmed symptomatic dengue infection for all seasons combined	All confirmed acute cases during the study period	Total person-years at risk, i.e. from enrolment until the first RT-qPCR confirmed symptomatic dengue infection, the end of the study or withdrawal, whichever comes first.
Incidence rate of laboratory confirmed or probable symptomatic dengue infections	All symptomatic dengue infections (including laboratory-confirmed and probable cases) during the period.	Total person-years at risk*.
Incidence rate of probable symptomatic dengue infection	All probable symptomatic dengue infection	Total person-years at risk*.
Proportion of subjects with primary inapparent dengue infection	All dengue IgG positive cases at the considered visit	Total number of IgG negative subjects at the previous visit
Proportion of subjects with secondary symptomatic dengue infection	All symptomatic infection since the previous visit	Total number of IgG positive subjects at the previous visit
Seroprevalence of dengue infection	All dengue IgG positive cases	Total number of subjects tested or previously positive

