6.9. Primary inapparent dengue infection

This condition is defined as a documented seroconversion (anti-dengue IgG antibodies) between two sequential sera samples obtained during the scheduled visits without clinical suspicion of dengue (identified during the time period in which seroconversion occurred).

Note that subjects with a visit for suspicion of dengue case (even with a negative result to acute and convalescent blood sample) won't be considered for inapparent infection.

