The same analysis as describe above will also be generated by calendar year. For the analyses by calendar years the analysis periods will begin on 01-Jan and end on 31-Dec of the considered year.

In addition, the number of subjects at risk, the number of households with at least one event (i.e. laboratory-confirmed symptomatic dengue cases, laboratory-confirmed or probable symptomatic dengue cases, probable symptomatic dengue cases) and the total number of events reported during the follow-up period at risk will also be tabulated along with the incidence rates.

The following analyses will be performed by study site, gender and age category:

- The seroprevalence of dengue infection with 95% CI (refer to Section 12.1 for the methodology for computing 95%CI) will be calculated at Visit 1 (i.e. the number of subjects tested positive for dengue IgG at Visit 1 divided by the total number of subjects with dengue IgG results at Visit 1).
- The incidence proportion of subjects with primary inapparent dengue infection with 95% CI (refer to Section 12.1 for the methodology for computing 95%CI) will be estimated for each dengue season and overall. It will be estimated as the number of documented seroconversion (anti-dengue IgG antibodies) without clinical suspicion of dengue (identified during the time period in which seroconversion occurred, using the blood sampling dates) per total number of subjects at risk. The total number of subjects at risk will be calculated using dengue IgG results at the scheduled visits. Only subjects with available test results for two consecutive scheduled visits will be considered in the denominator by season. Only subjects negative for anti-dengue IgG antibodies at one visit will contribute for the following period of analysis. For overall seasons, only subjects with negative result for anti-dengue IgG antibodies at the scheduled visit planned before their first season follow-up and with either available anti-dengue IgG results for the scheduled visit planned after the last season or with positive result for anti-dengue IgG antibodies at any scheduled visits planned in between will be included in the denominator.

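### The calculation rule for primary inapparent dengue infection contradicts its definition: followed as written, it counts every IgG seroconverter, including those with suspected or symptomatic dengue

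*SAP*

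**What the plan says.** **Definition.** SAP Amendment 1, Section 6.9 (and protocol 5.7.1.8) requires a documented IgG seroconversion between two sequential scheduled samples, "without clinical suspicion of dengue (identified during the time period in which seroconversion occurred").

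**Calculation.** SAP Section 7.2.1 gives the proportion as "the number of dengue IgG positive cases and at the visit divided by the total number of subjects IgG negative at the previous visit". Words appear to be missing after the first *and*. Section 7.2.1 then refers the reader to Table 1 for endpoint numerators and denominators. In that table the numerator is "All dengue IgG positive cases at the considered visit" and the denominator is "Total number of IgG negative subjects at the previous visit". Protocol Section 8.5.2 and Table 16 carry the same text.

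**Testing.** Section 7 of the SAP says that from Visit 2 onwards "Dengue IgG ELISA will be available for subjects with IgG negative at the previous visit".

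**Status of the endpoint.** Primary inapparent infection remains a secondary objective (SAP 3.2) and a secondary endpoint (SAP 4.2). Section 7.2.2, which lists the changes made in Amendment 1, gives no other rule for it.

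**Intent.** The superseded SAP of 14 June 2019 put the condition into the calculation itself (its Section 7.4): "It will be estimated as the number of documented seroconversion (anti-dengue IgG antibodies) without clinical suspicion of dengue". It also set a denominator condition: "Only subjects with available test results for two consecutive scheduled visits will be considered in the denominator by season". Neither was carried into Amendment 1, and neither Section 1 nor Section 10 of Amendment 1 mentions the difference. This older text is cited only as evidence of intent; the contradiction lies within the current documents.

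**The concern.** An endpoint defined by the absence of clinical suspicion has a formula that never checks for it. A programmer working from Table 1 and one working from 6.9 would get different counts whenever a seroconverter had a suspected dengue episode in the interval. The Table 1 result would carry the name inapparent infection while including subjects whose first infection was clinically recognised. The same subjects could also be counted as symptomatic cases elsewhere in the report, although Section 7.3.2 lists inapparent as a laboratory diagnosis distinct from the confirmed categories.

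**Working it through.** The documents state no figure for the inapparent proportion, so there is none to reproduce. The check is of what each rule counts, and then of how far the two can differ.

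**Step 1: what Table 1 counts.** Only previous negatives are retested, so every new positive is a seroconverter. With S seroconverters and N subjects IgG negative at the previous visit, Table 1 gives S/N, which is total seroconversion.

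**Step 2: what 6.9 counts.** With s the share of seroconverters who had clinical suspicion in the interval, 6.9 on the same denominator gives S(1−s)/N. The ratio of Table 1 to 6.9 is 1/(1−s).

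**Step 3: the denominator.** Table 1 does not require a result at the considered visit, and SAP 11.2 makes no provision for missing data. If a fraction d of N is not retested, 6.9 applied to retested subjects gives S(1−s)/[N(1−d)]. The ratio becomes (1−d)/(1−s), which exceeds 1 only when s is greater than d.

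Neither s nor d is given. For d, the table borrows the planned annual drop-out of 15 to 20% (protocol 8.2.1); s is varied.

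| s (assumed) | Same denominator, 1/(1−s) | d = 15% | d = 20% |
|---|---|---|---|
| 5% | 1.05 | 0.89 | 0.84 |
| 10% | 1.11 | 0.94 | 0.89 |
| 20% | 1.25 | 1.06 | 1.00 |
| 30% | 1.43 | 1.21 | 1.14 |
| 50% | 2.00 | 1.70 | 1.60 |

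**Step 4: a rough anchor for s.** Protocol 8.2.1 takes reported incidence as about 0.3% per year and under-reporting as a factor of 3: 0.3% × 3 = 0.9%, rounded there to about 1%. Assume that either rate applies to IgG negatives and that each such case seroconverts by the next visit. With total seroconversion of c per year (also assumed), the 6.9 figure is c minus the symptomatic rate:

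| c = Table 1 result | 6.9 result at 1% symptomatic | Ratio | 6.9 result at 0.3% symptomatic | Ratio |
|---|---|---|---|---|
| 2% | 1.0% | 2.00 | 1.7% | 1.18 |
| 3% | 2.0% | 1.50 | 2.7% | 1.11 |
| 5% | 4.0% | 1.25 | 4.7% | 1.06 |
| 10% | 9.0% | 1.11 | 9.7% | 1.03 |

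Clinical suspicion needs only a qualifying fever without an obvious other cause (SAP 6.1). It can therefore cover more seroconverters than confirmed or probable dengue does, and s may be larger than these anchors imply.

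**The case against.** The strongest reply is that 6.9 already governs. It stands in the same SAP, the Table 1 row is labelled with the term it defines, and Table 1 is shorthand elsewhere: the row for secondary symptomatic infection also drops the word secondary from its numerator. Sections 7.2.2 and 7.3.2 treat symptomatic and inapparent infection as separate. Section 7.2.1 is headed as a restatement of the protocol, and 7.2.2 then removes the analyses by season and those by seroprevalence at each visit, so the per-visit proportion may not be produced at all. The table templates are not available to settle that.

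Much of this stands. A reader might infer that the reported proportion will be total seroconversion; with 6.9 in force, the documents do not establish that. It does not remove the contradiction, however. For secondary infection, the text of 7.2.1 supplies the restriction that the table omits. For inapparent infection, the text omits it too. Nothing ranks 6.9 above Table 1, and the removals in 7.2.2 do not name this endpoint.

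Three further inferences are not supported:

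- *That the figure must be too high.* This holds only on a fixed denominator; Step 3 shows that untested subjects can cancel or reverse it.
- *That a ratio of inapparent to symptomatic infection will be biased.* Neither document plans one, and SAP Section 8 calls all analyses descriptive.
- *That dropping the June 2019 note to 6.9 is itself an error.* That note disqualified anyone with a suspected-dengue visit, "even with a negative result to acute and convalescent blood sample". Restoring it is a choice: it would also remove a subject who had an unrelated febrile illness and later seroconverted silently.

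Section 7.2.2 also reports few dengue episodes and many subjects IgG positive at Visit 1, so the number of subjects affected may be small.

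**Conclusion.** Wrong as written. The only current calculation rule for a retained secondary endpoint contradicts that endpoint's definition. If it is followed, the numerator is all IgG seroconverters, inflated by 1/(1−s) on a fixed denominator: 1.05 at s = 5%, 1.25 at 20%, 2 at 50%. All values of s are assumptions.

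The literal denominator is a second defect in the same row and acts in the opposite direction. With 15 to 20% not retested, the net ratio is 0.94 to 0.89 at s = 10% and 1.06 to 1.00 at s = 20%. The mismatch between rule and definition is therefore certain; the net direction and size of the error are not.

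**What to change.** In SAP 7.2.1 and Table 1:

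- **Numerator:** subjects with IgG seroconversion between two consecutive scheduled samples and no suspected dengue case with onset between the two sampling dates. The start date in 6.1 can serve as onset.
- **Denominator:** subjects IgG negative at the previous visit who have an IgG result at the considered visit.
- **Clinical suspicion:** state in 6.9 whether laboratory-negative suspected cases count, and whether suspected cases without documented fever count. Section 6.1 ignores the latter in the symptomatic analyses but is silent on this endpoint.
- **Optional:** show total seroconversion as a separate, labelled row.

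Repair the incomplete sentence in 7.2.1, and record in Section 10 that protocol Table 16 is replaced for this row. If 7.2.2 was meant to drop the per-visit proportion, say so and name what now answers the objective.

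The cost is SAP wording and a program filter on data already held (IgG results, sampling dates and suspected-case records). No new data are needed.

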7.2.2. Additional considerations

7.2.2.1. Incidence rate

In light of the low number of dengue episodes, the large number of positive anti-dengue IgG at visit 1 and the number of dengue cases reported outside the season,

1. The analyses of PCR confirmed cases (only 10 cases) and the analyses of secondary dengue infections were removed.
2. The analyses by seroprevalence at each visit were removed,
3. The analyses by season were removed. Only the analyses by calendar year are to be conducted

- 4. Subjects without seroprevalence status at visit 1 were removed from the ATP cohort because serological status of symptomatic/inapparent dengue infections cannot be assessed properly for such subjects
- 5. Planned analyses of medical and vaccination history were removed.
- 6. The statistical method was updated to ignore the household cluster effect and to provide incidence rate with confidence interval in absence of dengue episodes in a calendar year for a study site .

Regarding the last point, the expected annual incidence rate for a cohort of subjects followed over a full calendar will be computed using a log-linear model with the number of dengue events (all cases) as depend variable and the total number of subject-month as offset. The model will include the study site, year and month as independent categorical fixed effects (see below).

The expected annual incidence rate in a study site for each year will be estimated as the average of incidence rate over months

```

proc genmod ;
  class center month year;
  model evt= center year month /
    dist=poisson link=log offset=ln TYPE3;

  ods output Estimates=estimc;
  estimate 'center PPD 2014' intercept 12 center 12 0 0 0 0
    year 12 0 0 0 0
    Month 1 1 1 1 1 1 1 1 1 1 1;
  estimate 'center PPD 2014' intercept 12 center 0 12 0 0 0
    year 12 0 0 0 0
    Month 1 1 1 1 1 1 1 1 1 1 1;
  estimate 'center PPD 2014' intercept 12 center 0 0 12 0 0
    year 12 0 0 0 0
    Month 1 1 1 1 1 1 1 1 1 1 1;
  estimate 'center PPD 2014' intercept 12 center 0 0 0 12 0
    year 12 0 0 0 0
    Month 1 1 1 1 1 1 1 1 1 1 1;
  estimate 'center PPD 2014' intercept 12 center 0 0 0 0 12
    year 12 0 0 0 0
    Month 1 1 1 1 1 1 1 1 1 1 1;
  estimate 'overall 2014' intercept 12 center 2.4 2.4 2.4 2.4 2.4
    y 12 0 0 0 0
    Month 1 1 1 1 1 1 1 1 1 1 1;
  estimate 'center PPD 2015' intercept 12 center 12 0 0 0 0
    year 0 12 0 0 0
    Month 1 1 1 1 1 1 1 1 1 1 1;
  estimate 'center PPD 2015' intercept 12 center 0 12 0 0 0
    year 0 12 0 0 0
    Month 1 1 1 1 1 1 1 1 1 1 1;
  estimate 'center PPD 2015' intercept 12 center 0 0 12 0 0
    year 0 12 0 0 0
    Month 1 1 1 1 1 1 1 1 1 1 1;
  estimate 'center PPD 2015' intercept 12 center 0 0 0 12 0
    year 0 12 0 0 0
    Month 1 1 1 1 1 1 1 1 1 1 1;
  estimate 'center PPD 2015' intercept 12 center 0 0 0 0 12
    year 0 12 0 0 0

```

CONFIDENTIAL

116606 (EPI-DENGUE-006 BOD BR)
Statistical Analysis Plan Amendment 1

```
Month 1 1 1 1 1 1 1 1 1 1 1 1;
estimate 'overall 2015' intercept 12 center 2.4 2.4 2.4 2.4 2.4
year 0 12 0 0 0
Month 1 1 1 1 1 1 1 1 1 1 1 1;
estimate 'center PPD 2016' intercept 12 center 12 0 0 0 0
year 0 0 12 0 0
Month 1 1 1 1 1 1 1 1 1 1 1 1;
estimate 'center PPD 2016' intercept 12 center 0 12 0 0 0
year 0 0 12 0 0
Month 1 1 1 1 1 1 1 1 1 1 1 1;
estimate 'center PPD 2016' intercept 12 center 0 0 12 0 0
year 0 0 12 0 0
Month 1 1 1 1 1 1 1 1 1 1 1 1;
estimate 'center PPD 2016' intercept 12 center 0 0 0 12 0
year 0 0 12 0 0
Month 1 1 1 1 1 1 1 1 1 1 1 1;
estimate 'center PPD 2016' intercept 12 center 0 0 0 0 12
year 0 0 12 0 0
Month 1 1 1 1 1 1 1 1 1 1 1 1;
estimate 'overall 2016' intercept 12 center 2.4 2.4 2.4 2.4 2.4
y 0 0 12 0 0
Month 1 1 1 1 1 1 1 1 1 1 1 1;
estimate 'center PPD 2017' intercept 12 center 12 0 0 0 0
year 0 0 0 12 0
Month 1 1 1 1 1 1 1 1 1 1 1 1;
estimate 'center PPD 2017' intercept 12 center 0 12 0 0 0
year 0 0 0 12 0
Month 1 1 1 1 1 1 1 1 1 1 1 1;
estimate 'center PPD 2017' intercept 12 center 0 0 12 0 0
year 0 0 0 12 0
Month 1 1 1 1 1 1 1 1 1 1 1 1;
estimate 'center PPD 2017' intercept 12 center 0 0 0 12 0
year 0 0 0 12 0
Month 1 1 1 1 1 1 1 1 1 1 1 1;
estimate 'center PPD 2017' intercept 12 center 0 0 0 0 12
year 0 0 0 12 0
Month 1 1 1 1 1 1 1 1 1 1 1 1;
estimate 'overall 2017' intercept 12 center 2.4 2.4 2.4 2.4 2.4
year 0 0 0 12 0
Month 1 1 1 1 1 1 1 1 1 1 1 1;
estimate 'center PPD 2018' intercept 12 center 12 0 0 0 0
year 0 0 0 0 12
Month 1 1 1 1 1 1 1 1 1 1 1 1;
estimate 'center PPD 2018' intercept 12 center 0 12 0 0 0
year 0 0 0 0 12
Month 1 1 1 1 1 1 1 1 1 1 1 1;
estimate 'center PPD 2018' intercept 12 center 0 0 12 0 0
year 0 0 0 0 12
Month 1 1 1 1 1 1 1 1 1 1 1 1;
estimate 'center PPD 2018' intercept 12 center 0 0 0 12 0
y 0 0 0 0 12
Month 1 1 1 1 1 1 1 1 1 1 1 1;
estimate 'center PPD 2018' intercept 12 center 0 0 0 0 12
year 0 0 0 0 12
Month 1 1 1 1 1 1 1 1 1 1 1 1;
estimate 'overall 2018' intercept 12 center 2.4 2.4 2.4 2.4 2.4
year 0 0 0 0 12
Month 1 1 1 1 1 1 1 1 1 1 1 1;
```

```

estimate 'overall' intercept 60 center 12 12 12 12 12
                        year 12 12 12 12 12
                        Month 5 5 5 5 5 5 5 5 5 5 5 5;
estimate 'overall center PPD' ' intercept 60 center 60 0 0 0 0
                        year 12 12 12 12 12
                        Month 5 5 5 5 5 5 5 5 5 5 5 5;
estimate 'overall center PPD' ' intercept 60 center 0 60 0 0 0
                        year 12 12 12 12 12
                        Month 5 5 5 5 5 5 5 5 5 5 5 5;
estimate 'overall center PPD' ' intercept 60 center 0 0 60 0 0
                        year 12 12 12 12 12
                        Month 5 5 5 5 5 5 5 5 5 5 5 5;
estimate 'overall center PPD' ' intercept 60 center 0 0 0 60 0
                        year 12 12 12 12 12
                        Month 5 5 5 5 5 5 5 5 5 5 5 5;
estimate 'overall center PPD' ' intercept 60 center 0 0 0 0 60
                        year 12 12 12 12 12
                        Month 5 5 5 5 5 5 5 5 5 5 5 5;

run;
    
```

```

data estimc; set estimc;
    if label='overall' or index(label,'overall center') then do;
        estimate=exp(lbetaestimate/60);
        lower=exp(lbetalowercl/60);
        upper=exp(lbetauppercl/60);
        end;
    else do;
        estimate=exp(lbetaestimate/12);
        lower=exp(lbetalowercl/12);
        upper=exp(lbetauppercl/12);
        end;
run;
    
```

In case of subgroup analysis by gender or by age at visit 1 (<=17years, 18-49 years and >= 50years) or in case the model does not allow estimating confidence interval (eg problem of convergence or situation where there is no event in a site, in a calendar year or in a month) CI will be computed using exact CI based on a Poisson Distribution.

The following case provides the SAS code for the exact CI for incidence rate per subject-year when there are 14 events and 400 subject-years:

```

data check;
    fu=400;
    n=14;
    Rate=n/fu;
    LL_rate= GAMINV(0.025, n)/fu;
    UL_rate= GAMINV(0.975, (n+1))/fu;
    LL_rate_=cINV(0.025, 2*n)/(2*fu);
    UL_rate_=cINV(0.975, 2*n+2)/(2*fu);
    
```

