3.2. Secondary objectives

- To estimate the serotype-specific incidence of virologically-confirmed symptomatic dengue infection in the study population overall and by season.
- To estimate the incidence of symptomatic dengue infection (including laboratory-confirmed and probable cases) in the study population by study site, gender, age-group, previous dengue exposure (primary or secondary), overall and by season.
- To estimate the prevalence of previous dengue infection (dengue seroprevalence) in the study population overall and by study site, gender and age-group at enrolment.
- To estimate the incidence of primary inapparent dengue infection, in the study population overall and by study site, gender age-group and by season.
- To describe symptoms and spectrum of dengue disease in the study population.

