6.3. Virologically confirmed symptomatic dengue infection

A virologically confirmed symptomatic dengue infection is defined as a dengue case confirmed by RT-qPCR.

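### The RT-qPCR-confirmed incidence analyses are removed for having 10 cases, so a retained secondary objective gets no estimate although an exact interval is available

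*SAP*

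**What the plan says.** SAP Amendment 1, section 3.2, opens its secondary objectives with: "To estimate the serotype-specific incidence of virologically-confirmed symptomatic dengue infection in the study population overall and by season". Section 4.2 keeps the DENV-type-specific endpoints, and 6.3 fixes the case definition: "A virologically confirmed symptomatic dengue infection is defined as a dengue case confirmed by RT-qPCR".

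Section 7.2.2.1 lists the changes from plan. The lead-in begins "In light of the low number of dengue episodes, the large number of positive anti-dengue IgG at visit 1" and adds that cases occurred outside the season. The first item is "The analyses of PCR confirmed cases (only 10 cases) and the analyses of secondary dengue infections were removed". Section 1 carries the same list and section 10 points to both places.

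Later in 7.2.2.1, for gender or age subgroups and for situations where the Poisson model cannot give an interval (including no event in a site, year or month), "CI will be computed using exact CI based on a Poisson Distribution". SAS code follows, with "LL_rate= GAMINV(0.025, n)/fu" and "UL_rate= GAMINV(0.975, (n+1))/fu".

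RT-qPCR cases survive in two places. They are one route to laboratory confirmation in 6.2, and a laboratory-diagnosis category in the clinical summary of 7.3.2. Neither yields a virologically confirmed rate, an interval or a split by DENV type.

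**The concern.** An objective is kept while the only analysis that would answer it is taken out, and the note attached to the removal is the observed number of cases. All analyses are descriptive (SAP section 8), so there is no test or power threshold that 10 events would fail. For a study whose rationale (protocol 1.2) is to check attack-rate assumptions, a low virologically confirmed rate with its upper limit is a result. Without it, the report can give neither the overall rate of RT-qPCR-confirmed dengue nor any statement on how it divides among the four types.

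**Working it through.** **Inputs.** Events: n = 10 (SAP 7.2.2.1). Method: the exact Poisson code in 7.2.2.1, two-sided 95%. Person-years (PY): not stated in the documents, so assumed below.

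**Formula.** Lower = χ²(0.025; 2n) / (2·PY); upper = χ²(0.975; 2n+2) / (2·PY). This is the SAP's code in its chi-square form; the gamma form is identical.

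**Reproducing the documents' own figures.**
- Protocol Table 15, 10 cases in 3322.7 PY: stated exact interval 1.4 to 5.6 per 1000; recomputed 1.44 to 5.53.
- Protocol Table 15, 10 cases in 1661.3 PY: stated 2.8 to 11.1; recomputed 2.89 to 11.07.
- Both agree within 0.1. The protocol therefore already tabulated exact intervals at this very count.
- The SAP's example, "exact CI for incidence rate per subject-year when there are 14 events and 400 subject-years", prints no result. It gives 0.035 (0.0191 to 0.0587), and both code forms agree.

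**Ten events.** χ²(0.025; 20)/2 = 4.80 and χ²(0.975; 22)/2 = 18.39. Divided by 10, the limits are 0.48 and 1.84 times the rate, whatever the follow-up.

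**Range of person-years.** The table in SAP section 7 gives seasons covered: Rio 4, Manaus 4, Salvador 3, Natal 2, Campinas 1, in total 14 site-seasons. Taking one site-season as one year of follow-up at a site:
- 500 subjects with Table 15 drop-out: 14 × 461.5 = 6,461, about 6,500 PY.
- 600 subjects with no drop-out: 14 × 600 = 8,400 PY.

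| Assumed PY | Rate per 1000 | Exact 95% CI |
|---|---|---|
| 6,500 | 10/6.5 = 1.54 | 4.80/6.5 = 0.74 to 18.39/6.5 = 2.83 |
| 8,400 | 10/8.4 = 1.19 | 4.80/8.4 = 0.57 to 18.39/8.4 = 2.19 |

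**By DENV type** (the split is not given; illustrative counts at 6,461 PY, per 1000). No case: upper limit 0.57. Three cases: 0.46 (0.10 to 1.36). Five cases: 0.77 (0.25 to 1.81).

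**Clustering.** Scaling events and person-years by the protocol's design effect of 1.8 (8.2.2), so an effective count of 10/1.8 = 5.6, widens the overall interval to 0.54 to 3.47 at 6,461 PY and 0.45 to 2.89 at 7,753 PY (14 × 553.8). It is wider, but still reportable.

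**Fit with the SAP's own rule.** The main model has 1 + 4 + 4 + 11 = 20 parameters (intercept, site, year, month). Ten events cannot fall in all 12 months, so at least two months are empty. That is a situation for which 7.2.2.1 itself prescribes the exact interval.

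**The case against.** The strongest reply is that this is a disclosed reduction of scope. Section 3 repeats the protocol's objectives wholesale, including tertiary ones that 7.4 says will not be analysed, so being listed in 3.2 proves little. The removal is stated with reasons in sections 1 and 7.2.2.1 and referenced in section 10. The sponsor had ended its vaccine programme. Ten cases over up to four types say little beyond the counts. The table templates are not part of the documents, so DENV type may appear in a listing.

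Much of this stands. A reader might infer concealment; the documents show the opposite. A reader might also infer that the most specific case definition has left the study. It has not, because RT-qPCR positivity still defines laboratory-confirmed cases and is a category in 7.3.2.

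The same sentence removes secondary infections, and a reader might infer that an incidence split by previous exposure must come back too, on the ground that most cases fall there. The documents do not support that. They give no case split by exposure. The removed item could be the visit-based proportion, the incidence by exposure, or both. Exposure status changes over follow-up and would need new derivation. Probable cases rest on IgG, and the protocol's amendment rationale warns that Zika antibodies can cross-react in dengue serology.

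What the reply does not meet is the gap itself. For the tertiary objectives the SAP says outright that they will not be analysed; for this secondary objective it says nothing of the kind. The other lead-in reasons, seropositivity at Visit 1 and cases outside the season, do not prevent an all-years RT-qPCR rate.

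**Conclusion.** The point holds in a limited form. A retained secondary objective gets no rate or interval, through a declared change that cites the observed count, and that count is no obstacle to estimation. The firm figure is the relative width, 0.48 to 1.84 times the rate, which depends only on n = 10 and the Poisson assumption. The absolute rate of about 1.2 to 1.5 per 1000 person-years, with limits from 0.6 to 2.8, rests on assumed follow-up of 6,500 to 8,400 person-years. A larger total such as 10,000 is not plausible for 14 site-seasons with one planned site never opened. The primary endpoint is unaffected. Because nothing is tested, the post-data choice raises a question of complete reporting and not of type I error.

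**What to change.** Reinstate one table covering all years: RT-qPCR-confirmed cases, person-years, rate per 1000 and exact Poisson 95% CI, overall and by DENV type. SAP 7.2.1 already ends time at risk at the first RT-qPCR-confirmed infection, so the denominator is defined. Set the lower limit explicitly to 0 for a type with no case, since the gamma quantile with shape 0 is undefined. Add a row for positives that could not be typed, which the assay table in section 7 allows for.

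Footnote that the interval ignores household clustering and that by-type cells are sparse. Season splits can stay out; section 10 should say that the by-season part of the objective is not addressed.

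The cost is one table from data and code already in hand, and the price is wide intervals. If the sponsor declines, the minimum is a sentence in 3.2 and section 10 stating that this objective will not be estimated.
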